| Adverse event monitoring | X | X | X | X | X | | 
Screening to randomization: All AEs, SAEs, and other reportable events that cause the participant to be excluded from the trial or are the result of a protocol-specified intervention are to be reported.
 
Randomization through 14 days following Dose 3: AEs (serious and non-serious) are to be reported from Days 1 through 14 following each vaccination. SAEs, deaths, other reportable events (ie, cancer, overdose, pregnancy, and infant SAEs) are to be reported throughout the duration of an individual's study participation. Exposure during breastfeeding is to be reported from Day 1 through Month 7.
 |
| Review of eVRC data | | | X | X | X | | |
| Reminder contact for urine/saliva self-collection and pregnancy status | | | | | | X | |
| Urine and saliva for CMV | | X | Collected monthly | | | | Self-collected by participant starting at Day 1 (prior to vaccination) and then continue monthly through ~Month 36 or beyond, depending on event accrual |

Vacc = Vaccine; eVRC = Electronic vaccination report card; NAbs = neutralizing antibodies; β-hCG = Human chorionic gonadotropin; IgG = immunoglobulin G; IFN-γ = Interferon gamma; ELISA = Enzyme-linked immunosorbent assay; PBMC = peripheral blood mononuclear cell; DNA = Deoxyribonucleic acid; CMV = Cytomegalovirus; AE = Adverse event; SAE = Serious adverse event

2.2 Schedule of Activities: Follow-up Period Through Approximately Month 36 (Approximate Time Point to Reach Cases Required for Primary Endpoint Assessment)

| Trial period | Follow-up period | | | | | Reminder contacts (monthly) | Notes |
|------------------------------------------------------------------------------------------------------------------------------------------------|-------------------------------|---------------------------------|-------------------------------|---------------------------------|--------------------------------|-----------------------------|-----------------------------------------------------------------------------------------------------------------------------------------------------------------------------------------------------------------------------------------------------------------------------------------------------------------------------------------------|
| Visit number/title | Visit 6 Month 12 Year 1 | Visit 7 Month 18 Year 1.5 | Visit 8 Month 24 Year 2 | Visit 9 Month 30 Year 2.5 | Visit 10 Month 36 Year 3 | | |

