8.1 Discontinuation of Study Treatment

Discontinuation of study treatment does not represent withdrawal from the study.

As certain data on clinical events beyond study treatment discontinuation may be important to the study, they must be collected through the participant's last scheduled follow-up, even if the participant has discontinued study treatment. Therefore, all participants who discontinue study treatment prior to completion of the vaccination regimen will still continue to participate in the study as specified in the SoA. This includes the self-collection of urine and saliva samples by study participants.

Participants may discontinue study treatment at any time for any reason or be dropped from the study treatment at the discretion of the investigator should any untoward effect occur. In addition, a participant may be discontinued from study treatment by the investigator or the Sponsor if study treatment is inappropriate, the trial plan is violated, or for administrative and/or other safety reasons. Specific details regarding procedures to be performed at study treatment discontinuation are provided in Section 9.1.9.

A participant must be discontinued from study treatment but continue to be monitored in the study for any of the following reasons:

- The participant or participant's legally acceptable representative requests to discontinue study treatment.
- The participant's treatment assignment has been unblinded by the investigator, Merck subsidiary or through the emergency unblinding call center.
- The participant has a medical condition or personal circumstance which, in the opinion of the investigator and/or sponsor, places the participant at unnecessary risk from continued administration of study treatment.
- The participant has a confirmed positive pregnancy test.
- The participant had an allergic reaction or an anaphylactic/anaphylactoid reaction that required medical intervention following Dose 1 administration.
- The participant enrolled in another interventional clinical trial following Dose 1 administration.
- Received a non-study CMV vaccine.

For participants who are discontinued from study treatment but continue to be monitored in the trial, all visits and procedures, as outlined in the SoA, should be completed.

Discontinuation from study treatment is "permanent." Once a participant is discontinued, she shall not be allowed to restart study treatment.

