9.3 Adverse Events (AE), Serious Adverse Events (SAE) and Other Reportable Safety Events

The definitions of an adverse event (AE) or serious adverse event (SAE), as well as the method of recording, evaluating, and assessing causality of AE and SAE and the procedures for completing and transmitting AE, SAE and other reportable safety event reports can be found in Appendix 4.

AE, SAEs, and other reportable safety events will be reported by the participant (or, when appropriate, by a caregiver, surrogate, or the participant's legally authorized representative).

The investigator, who is a qualified physician, and any designees are responsible for detecting, assessing, documenting, and reporting events that meet the definition of an AE or SAE as well as other reportable safety events. Investigators remain responsible for following up AE, SAEs and other reportable safety events for outcome according to Section 9.3.3.

9.3.1 Time Period and Frequency for Collecting AE, SAE and Other Reportable Safety Event Information

All AEs, SAEs and other reportable safety events that occur after the consent form is signed but before allocation/randomization must be reported by the investigator if they cause the participant to be excluded from the trial, or are the result of a protocol-specified intervention, including but not limited to washout or discontinuation of usual therapy, diet, placebo treatment or a procedure.

From the time of allocation/randomization through 14 days following the first vaccination(s) and from the time of any subsequent vaccination(s) through 14 days thereafter, all AEs, SAEs and other reportable safety events must be reported by the investigator. SAEs (regardless of causality), other reportable safety events (ie, Cancer, Overdose, pregnancy, and infant SAEs) are reportable throughout the duration of an individual's study participation. Exposure during breast feeding is reportable from Day 1 through Month 7.

Additionally, any SAE brought to the attention of an investigator at any time outside of the time period specified in the previous paragraph also must be reported immediately to the Sponsor if the event is either:

1. A death that occurs prior to the participant completing the trial, but outside the time period specified in the previous paragraph.

or

2. A serious adverse event that is considered by an investigator who is a qualified physician to be vaccine related.

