Investigators are not obligated to actively seek AE or SAE or other reportable safety events in former study participants. However, if the investigator learns of any SAE, including a death, at any time after a participant has been discharged from the study, and he/she considers the event to be reasonably related to the study treatment or study participation, the investigator must promptly notify the sponsor.

All initial and follow-up AEs, SAEs and other reportable safety events will be recorded and reported to the sponsor or designee within the timeframes as indicated in [Table 4](#).

Table 4 Reporting Time Periods and Timeframes for Adverse Events and Other Reportable Safety Events

| Type of Event | Reporting Time Period: Consent to Randomization/ Allocation | Reporting Time Period: Randomization/ Allocation through Protocol- Specified Follow- up Period | Reporting Time Period: After the Protocol Specified Follow- up Period | Timeframe to Report Event and Follow-up Information to SPONSOR: |
|-----------------------------------------|-----------------------------------------------------------------------------------------------------------------------------------------------------|-------------------------------------------------------------------------------------------------------------------------|------------------------------------------------------------------------------------------------------------------------|--------------------------------------------------------------------------|
| Non-Serious Adverse Event (NSAE) | Report if: - due to protocol-specified intervention - causes exclusion - participant is receiving placebo run-in or other run-in treatment | Report all from the time of each vaccination through 14 days thereafter. | Not required | Per data entry guidelines |
| Serious Adverse Event (SAE) | Report if: - due to protocol-specified intervention - causes exclusion - participant is receiving placebo run-in or other run-in treatment | Report all for the duration of an individual's study participation. | Report if: - drug/vaccine related. - any death until participant completion of trial (Follow ongoing to outcome) | Within 24 hours of learning of event |
| Pregnancy | Report if: - due to intervention - causes exclusion | Report all – Follow to completion/termination and report outcome | Previously reported – Follow to completion/termination; report outcome | Within 24 hours of learning of event |

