10.6.3 Statistical Methods for Safety Analyses

Safety and tolerability will be assessed by clinical review of all relevant parameters including AEs and outcomes of pregnancies.

The analysis of safety results will follow a tiered approach ([Table 5](#)). The tiers differ with respect to the analyses that will be performed. Safety parameters or adverse events of special interest that are identified *a priori* constitute “Tier 1” safety endpoints that will be subject to inferential testing for statistical significance with p-values and 95% confidence intervals provided for between-group comparisons. Other safety parameters will be considered Tier 2 or Tier 3. Tier 2 parameters will be assessed via point estimates with 95% confidence intervals provided for V160 dose regimen versus placebo comparisons; only point estimates by treatment group are provided for Tier 3 safety parameters. Safety results will be summarized for each vaccination dose and across all three vaccination doses.

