Vaccine-type viral shedding will be assessed in V160-vaccinated participants. In addition to the analysis strategy shown in [Table 5](#), point and corresponding 95% CI estimates of incidence of vaccine-type viral shedding (number of participants observed with vaccine-type viral shedding/total person-years of follow-up) will be calculated separately for the V160 3-dose, V160 2-dose, and placebo arms. No treatment group comparisons (V160 vs. placebo or V160 3-dose vs. 2-dose arms) of the percent of participants detected with vaccine-type viral shedding will be conducted.

Summaries of SAEs (throughout the study duration) by system organ class will be provided as incidence rates (number of participants [or infants] observed with a specific SAE/total person-years of follow-up) rather than percentages.

Table 5 Analysis Strategy for Safety Parameters

| Safety Tier | Safety Endpoint | p-value | 95% CI for Comparison of V160 to Placebo | Descriptive Statistics |
|-------------|-------------------------------------------------------------------------------|---------|------------------------------------------|------------------------|
| Tier 2 | Solicited injection site AEs ^a | | X | X |
| | Solicited systemic AEs | | X | X |
| | Vaccine-related systemic AEs | | X | X |
| | Any serious AEs (in study participants or infants born to study participants) | | X | X ^b |
| | Vaccine-related serious AEs within Days 1 through 14 after vaccination | | X | X |
| | Discontinuations due to AEs | | X | X |
| | Elevated temperature ^c | | X | X |
| | AEs by SOC observed in ≥7 participants in at least one vaccination group | | X | X |
| Tier 3 | AEs by SOC | | | X |
| | Outcomes of pregnancies | | | X |
| | Vaccine-type viral shedding | | | X [‡] |

^a All injection site AEs are considered vaccine-related.
^b Incidence rates (cases/total person-years follow-up) will be provided instead of percentages.
^c Defined as ≥38.0°C [≥100.4°] oral or equivalent
 AE = Adverse event; CI = Confidence interval; SOC = System organ class; X = indicated summary statistic will be provided.

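### Non-serious AEs that start more than 14 days after a dose and lead to stopping vaccination need not be reported, so the Tier 2 row for AE-related discontinuations can undercount them

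*Combined protocol and SAP*

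**What the plan says.** **Collection.** Three places set the period for non-serious AEs after randomization, and they agree.

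- Protocol Table 4, non-serious AE row: "Report all from the time of each vaccination through 14 days thereafter".
- Protocol 9.3.1, text: "from the time of any subsequent vaccination(s) through 14 days thereafter, all AEs, SAEs and other reportable safety events must be reported".
- Schedule of Activities 2.1, note on AE monitoring: "AEs (serious and non-serious) are to be reported from Days 1 through 14 following each vaccination".

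SAEs and the other reportable events (cancer, overdose, pregnancy, infant SAEs) are treated differently: they "are reportable throughout the duration of an individual's study participation".

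**Stopping.** Section 8.1 allows a participant to "be dropped from the study treatment at the discretion of the investigator should any untoward effect occur". It also lists reasons for mandatory discontinuation, including medical conditions. Neither provision is tied to the days after a dose.

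**Analysis.** Protocol Table 5 lists "Discontinuations due to AEs" in Tier 2, and sSAP 3.6.3, Table 1 repeats the row. Section 10.6.3 says what the tier means: "Tier 2 parameters will be assessed via point estimates with 95% confidence intervals provided for V160 dose regimen versus placebo comparisons". The row carries no time window, whereas another Tier 2 row in the same table does: "Vaccine-related serious AEs within Days 1 through 14 after vaccination".

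**The concern.** The analysis row asks for all discontinuations due to AEs, while the collection rules supply only some of the AEs that could cause one. Suppose a non-serious condition begins on Day 30 after Dose 1 and the investigator stops vaccination for it. The site can follow every reporting rule and file no AE. A count built on AE records would then omit this participant from a comparison that a reader takes to be complete.

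Three features of the plan sharpen the mismatch.

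- The checks that lead to a stopping decision (the post-Dose 1 exclusion criteria and the directed physical examination) are made at Visits 3 and 4, long after the preceding 14-day window has closed.
- Table 4 already has a trigger of the kind that is missing. Before randomization, a non-serious AE is reportable if it causes exclusion. After randomization nothing similar applies to an AE that causes discontinuation.
- sSAP 3.5.1 removes from the per-protocol efficacy population anyone with an autoimmune diagnosis up to Month 7. The plan thus relies on such information beyond the windows in which a non-serious AE must be reported.

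Section 10.7.2 sends the 10.6.3 safety summaries to the eDMC, so this row is among what it sees. Such a row is likely to rest on small counts, where a few missing records could matter.

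**Working it through.** The documents give no figure for this gap, so there is none to reproduce. The check has three parts.

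**1. Is there a rule elsewhere that closes the gap?**

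- Section 7.6 requires written documentation when the vaccination plan is interrupted. That is a record of a decision, not an AE report, and nothing links it to the Table 5 row.
- Section 9.1.9 requires AEs present at withdrawal to be followed under Section 9.3. It does not widen the onset window.
- Section 9.3.3 requires non-serious AEs to be followed for outcome. An AE that starts inside a window and stops a later dose is therefore captured. One that starts outside is not.

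No other provision extends reporting to a late-onset, non-serious AE that ends dosing.

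**2. How much of the dosing period do the windows cover?**

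Inputs from Schedule of Activities 2.1: Dose 1 on Day 1, Dose 2 on Day 61 (±21 days), Dose 3 on Day 183 (±28 days). The window is 14 days per dose. After Dose 3 no dose remains to be stopped, so only the first two windows count.

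- Days on which a remaining dose can be stopped: 183 − 1 = 182.
- Days covered: 14 + 14 = 28. Coverage: 28/182 = 15.4%.
- Days uncovered: (61 − 1 − 14) + (183 − 61 − 14) = 46 + 108 = 154, or 154/182 = 84.6%.

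Across the visit windows, Dose 2 falls on Day 40 to 82 and Dose 3 on Day 155 to 211. Both 14-day windows always fit, so coverage depends only on the day of Dose 3:

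- Dose 3 on Day 155: 28/154 = 18.2%.
- Dose 3 on Day 211: 28/210 = 13.3%.

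If 14 days thereafter is read as 15 calendar days including the vaccination day, nominal coverage is 30/182 = 16.5%.

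The earliest permitted Visit 3 is Day 61 − 21 = 40, which is 39 days after Dose 1. A condition of recent onset found there is already outside the window.

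**3. How sensitive is such a row to a few missing records?**

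Protocol Table 8 gives a 95% CI of 0.1% to 1.7% for a 5:0 split with 700 per arm. A recalculation with the Miettinen and Nurminen method gives 0.17 to 1.66 percentage points for 5:0, and −0.12 to 1.25 for 3:0. If two of five such discontinuations in a V160 arm were missed, an interval that excludes zero would become one that includes it. This is an illustration only: the documents give no expected number of these events.

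**The case against.** The 14-day window is a reasoned choice. Section 5.4.1.3 bases it on when AEs peak after vaccination and on the vaccine's limited potential for replication. The row can also be read as computed from whatever AEs were collected, like the other AE rows. It is one descriptive Tier 2 row, with no p-value and no safety hypothesis behind it, and it is not named in the endpoint list of 10.4.3. Appendix 4 lets an investigator class an important medical event as serious by judgment, so some grave late-onset conditions would be reported by that route.

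Most of this stands, and it limits the point. It does not remove it. The rationale supports 14 days for general AE collection but does not address AEs that stop dosing. If the row is meant to cover only collected AEs, the table should say so, as it does for vaccine-related SAEs.

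A reader might infer more than the documents support:

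- *That any AE which stops dosing outside the windows goes unrecorded.* SAEs, cancer and overdose are reportable throughout. Onset governs reporting of non-serious AEs, not the day dosing stops. The interruption itself must be documented in writing. The text shows only that an AE report is not required.
- *That about 85% of such events are missed.* That figure is calendar time. Reactogenicity clusters early.
- *That the primary tolerability conclusion is undermined.* The primary safety endpoints are defined within Days 1-5 or 1-14, which collection covers.
- *That the comparison is tilted towards one arm.* The same rule applies in all arms under blinding, so the main effect is undercounting.
- *That the vaccine's replication raises the stakes.* Section 3.2.2.3 describes V160 as conditionally replication defective.

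**Conclusion.** The point holds in a narrow form. If the plan is followed exactly, non-serious AEs with onset more than 14 days after a dose that lead to stopping vaccination can be left out of a Tier 2 row that states no such limit.

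The exposed period is 154 of 182 days on the nominal schedule, with coverage between 13.3% and 18.2% across the visit windows. The share of discontinuing AEs affected is unknown and probably much smaller than the uncovered share of time.

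The conclusion assumes that the row is built from AE records, and that no data entry guideline outside these documents already asks for such reports. It is worth correcting because the correction is cheap, not because a main safety conclusion depends on it.

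**What to change.** In 9.3.1, in the non-serious AE row of Table 4 (the column from randomization through follow-up) and in the AE note of Schedule of Activities 2.1, add one sentence: any AE that leads to permanent discontinuation of study vaccination is reported, whatever its onset day, from randomization until the last scheduled dose. Then define the discontinuation row in protocol Table 5 and sSAP Table 1 on these records.

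If dosing is already complete, change only the label: state in both tables that, for non-serious AEs, the row is limited to onset on Days 1-14 after a dose.

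I would not extend the rule to AEs that lead to study withdrawal through study end. The follow-up schedule in 2.2 provides only for death and SAE monitoring, so that would be a larger change in collection.

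The cost is a matching line in the data entry guidelines and a few extra AE records, which must be tabulated separately from the Days 1-14 AEs. No visit is added, and the rules on who stops vaccination do not change.

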9.3.2 Method of Detecting AE, SAE and Other Reportable Safety Events

Care will be taken not to introduce bias when detecting AE and/or SAE and other reportable safety events. Open-ended and non-leading verbal questioning of the participant is the preferred method to inquire about AE occurrence.

9.3.3 Follow-up of AE, SAE and Other Reportable Safety Event Information

After the initial AE/SAE report, the investigator is required to proactively follow each participant at subsequent visits/contacts. All AE, SAE and other reportable safety events including pregnancy and exposure during breastfeeding, Cancer and Overdose will be followed until resolution, stabilization, until the event is otherwise explained, or the participant is lost to follow-up (as defined in Section 8.3). In addition, the investigator will make every attempt to follow all non-serious AEs that occur in randomized participants for outcome. Further information on follow-up procedures is given in Appendix 4. Although participants are to agree not to become pregnant during the vaccination period through Month 7, if a pregnancy is reported before the last planned V160/placebo dose, the participant will be discontinued from further planned vaccination regimen per exclusion criterion but will not be discontinued from the study. Participants who inadvertently become pregnant before receiving all 3 doses of study vaccine or placebo, and any participant who becomes pregnant after the treatment phase will remain in the trial for follow-up of pregnancy and outcome.

9.3.4 Regulatory Reporting Requirements for SAE

- Prompt notification (within 24 hours) by the investigator to the sponsor of SAE is essential so that legal obligations and ethical responsibilities towards the safety of participants and the safety of a study treatment under clinical investigation are met.
- The sponsor has a legal responsibility to notify both the local regulatory authority and other regulatory agencies about the safety of a study treatment under clinical investigation. All Adverse Events will be reported to regulatory authorities, IRB/IECs and investigators in accordance with all applicable global laws and regulations, ie, per ICH Topic E6 (R1) Guidelines for Good Clinical Practice.
- Investigator safety reports must be prepared for suspected unexpected serious adverse reactions (SUSAR) according to local regulatory requirements and sponsor policy and forwarded to investigators as necessary.
- An investigator who receives an investigator safety report describing an SAE or other specific safety information (eg, summary or listing of SAE) from the sponsor will file it along with the Investigator's Brochure and will notify the IRB/IEC, if appropriate according to local requirements.

